6. RISKS AND POTENTIAL BENEFITS

Subjects participating in this study are exposed to the same inherent risks shared by all patients undergoing treatment for SAH and who receive a lumbar drain as SOC for a number of clinical applications. These risks include but are not limited to headache, nausea/vomiting, transient pain, re-bleed, infection, CSF leak, changes in intracranial pressures, cognitive defects or poor neurological outcomes, other SAH complications and complications from associated interventions (e.g., IA therapy, angiography) and death.

The Study protocol does not prevent SOC for the management of SAH patients and utilizes well established techniques for lumbar puncture for diagnostic purposes, therapeutic applications or interventions. Only Investigators trained in the management of SAH patients, the associated care pathways and/or placement and management of lumbar drains are included in this study. Further, Investigators are trained on the Clinical Protocol to further minimize subject risks.

6.1 Risks Associated with the Device, Components or Procedure

The table below outlines the risks that are associated with the Neurapheresis System (catheter, components and study procedure). In the event of a catheter or disposable replacement, the risk profile remains unchanged.

Table 2:Neurapheresis System Risks

Risks
Additional radiation exposure
Brainstem herniation
Headache
Nausea / Vomiting
Fluctuation in CSF volume or pressure
CSF leak
Retained catheter
Localized transient pain (back/leg)
Peripheral neuropathy / Paralysis
Re-Bleed / Hemorrhage
Infection / Sepsis
Subdural spinal hematoma
Death

6.2 Potential Benefits

It is hypothesized that utilizing the Neurapheresis System post SAH could improve neurological outcomes by the rapid removal of the CSF contaminants (blood and those generated during the lysis of the subarachnoid hemorrhage¹¹). Other potential benefits may include a reduced likelihood

¹¹ Klimo et al., "Marked Reduction of Cerebral Vasospasm with Lumbar Drainage of Cerebrospinal Fluid after Subarachnoid Hemorrhage."

of common SAH complications. These benefits are only theoretical at this time; therefore, subjects may receive no direct benefit from participation in this study.

[figure not shown]

Figure 6: Expected PILLAR-XT Subject Flow

7. STUDY REQUIREMENTS

Once the subject or LAR provide consent, study data collection should begin as the subject is considered enrolled. The Investigator shall follow the institutional SOC for the treatment of SAH while providing the Sponsor with the data required for the study.

Outlined in Figure 6 is the PILLAR-XT Subject flow which describes how subjects would move through the study and the associated surveillance requirements. It is expected that subjects will participate in the study for a maximum of 36 days from the time of enrollment to the time of exit.

7.1 Screening Requirements

Standard of care assessments may be used to screen potential subjects against inclusion/exclusion (I/E) criteria for the study. Testing that is outside of SOC, cannot be performed until after a subject has been enrolled (i.e. written informed consent obtained). Once the subject has been enrolled and it has been determined that screening criteria are met, the subject can be prepared for catheter placement. If instead it is determined that a subject no longer meets study criteria after completing all screening assessments, they are to be withdrawn immediately and classified as an “Intent to Treat” subject. Enrollment data collected to that point and the reason for study exit should be entered into the case report forms for submission to the sponsor.

A screening CT is required to assess I/E criteria and is expected to be a SOC test for the diagnosis and treatment planning of aSAH. If a subject has been transferred from another institution at which a CT was obtained, a new screening CT is not required provided that an electronic copy of the CT can be obtained from the referring institution. It is expected that the volume of any identified mass lesions as noted in the study exclusion criteria will be calculated using the standard of care formula used by most radiologists in practice today. The formula should be based on the estimated volume of an ellipsoid ($L \times W \times H \times 0.52$ (where 0.52 is an approximation for $\pi/6$).

Volume = $A \times B \times C / 2$

- A = greatest hemorrhage diameter in the axial plane
- B = hemorrhage diameter at 90° to A in the axial plane
- C = originally described as the number of CT slices with hemorrhage multiplied by the slice thickness, but can simply be substituted with the craniocaudal diameter of the hemorrhage where there is access to multiplanar reformats

A venous blood sample is also required for screening and to establish baseline values for certain inflammatory markers (platelets and white blood cells including neutrophils and lymphocytes). Sample amounts should be based on site specific laboratory requirements for completion of tests including a Complete Blood Count (CBC) with Differentials and a Comprehensive Metabolic Panel (CMP). Current laboratory certificates are required by the sponsor with laboratory processes to be made available upon request.

7.2 Pre-Neurapheresis Imaging (CT) Requirements

As aneurysm securement (especially clipping) may change the amount of blood in the subarachnoid space, a CT is required following aneurysm securement but prior to beginning Neurapheresis. This CT will serve as the Baseline CT (pre-Neurapheresis CT) which, along with the screening CTs, will be compared to the post-Neurapheresis CTs. The Baseline CT is expected to be taken in a department scanner using optimal metal artifact reduction settings at the conclusion of aneurysm securement or following catheter insertion but prior to initiation of Neurapheresis therapy. The baseline CT must be reviewed to determine safety, via intracranial

stability, prior to beginning Neurapheresis therapy. In particular, the Investigator must assess the CT for the following criteria:

- no evidence of re-bleeding;
- no increasing mass effect;
- no effacement of the basilar cisterns;
- continued communication between the ventricles and subarachnoid space

In addition to the CT requirements above, study therapy cannot begin for at least 8 hours following aneurysm securement for subjects who underwent a clipping procedure.

If the subject meets these criteria, study therapy can be initiated. If the subject does not meet these criteria, either the subject can be exited, or another CT can be taken to determine baseline stability. If the subject still does not meet the safety criteria to begin study therapy after the second baseline CT, the subject is to be exited. If the study catheter was not placed prior to the baseline CT, the subject should be exited as an Intent to Treat Subject and no further follow-up is required. If however the study catheter was placed prior to the baseline CT, a 2-day follow-up is to be completed and the subject exited as an Attempt to Treat Subject.

7.3 Heparinization/Anti-Platelet Guidance/Aneurysm Stability

If Heparin is to be administered as a center SOC for a coiling procedure, study subjects must have a baseline Activated Clotting Time (ACT) drawn *prior to administration of the initial heparin* bolus. An additional ACT must be checked prior to the Neurapheresis catheter insertion. When the ACT reads baseline ± 10 sec it is deemed safe to proceed. ACT's must be recorded on the case report form and are considered to be source documentation if not captured elsewhere in the medical record.

If a subject requires an additional platelet aggregation inhibitor e.g., Integrilin as part of the coiling procedure, the Investigator may wait to insert the Neurapheresis catheter but must initiate catheter insertion *within the window of 48hours post ictus* and, coagulation is deemed safe to proceed. Subjects who are enrolled and do not meet these criteria of time or coagulation should be withdrawn and are classified as “Intent to Treat subjects”. Documentation of adequate coagulation metrics is a protocol requirement regardless of method used to secure the aneurysm.

Prior to proceeding with catheter insertion, the Investigator uses professional judgement to determine if the Subject and aneurysm is stable. If stability is in question, the Investigator may wait to insert the catheter but insertion must still fall within the 48 hour from ictus time frame.

7.4 Catheter Insertion

The Investigator should be mindful of a history of lumbar or thoracic stenosis or any existing spinal instrumentation when placing the catheter. Initial insertion of the investigational catheter is to be timed to be as close as possible to completion of the initial treatment/securement of the SAH but no later than 48 hours post-bleeding event. Ideally, the catheter should be inserted immediately after the coiling or clipping procedure; see the previous Section for guidance concerning Heparin and anti-platelet administration. Insertion of the Neurapheresis catheter is expected to have a similar pain profile as that of lumbar drain insertion and should be treated

accordingly. It is recommended that adequate local anesthetic and sedation/analgesia is in place at the time of catheter insertion. An MNeuro CFS will be onsite to support the catheter placement and system prep.

The Investigator may choose the position which affords the most technical comfort level for insertion e.g., lateral decubitus or prone; there is no protocol requirement for positioning, but the position of the subject must be documented on the Neurapheresis CRF. If the catheter placement occurs immediately following a clipping procedure, a C-arm and an OR table that can accommodate portable fluoroscopy will be needed. Continuous lateral fluoroscopy is recommended during guidewire insertion to ensure that there is no looping of guidewire and that catheter follows the guidewire appropriately and tracks dorsally. Elapsed time to place the catheter is a required data item.

Catheter insertion and system set up are to be performed according to the Instructions For Use (IFU). While highlights of the insertion are included in this protocol, the current IFU should be referenced prior to and/or during each procedure. Investigators delegated to perform catheter placement are required to acknowledge their review and understanding of the IFU prior to being approved to place the catheter. The investigational catheter is expected to be inserted under fluoroscopic guidance using the tools provided by the Sponsor, however if the subject anatomy is unusual, use of different delivery tools e.g., guidewires, and access needles may be allowed. Documentation on the case report forms will be required.

To minimize the risk of infection and nerve damage, insertion and placement of the catheter is limited to two (2) discrete events. If the catheter ceases to function effectively e.g., positional migration, kink or clot, the Investigator may remove the catheter once and replace it with another catheter. Subjects must be transported to an interventional procedure room for catheter replacement; re-insertion may not be facilitated at the bedside with a C-arm. The catheter change-out is to be performed according to the IFU. If a catheter change out is needed, it is required that the system disposables are also replaced to mitigate the risk of infection e.g., meningitis. Reconnecting to an existing system would result in a protocol deviation.

7.4.1 Catheter Insertion Highlights

- Soak and flush catheter in preservative free saline prior to insertion
- SOC patient prep, positioning and anesthesia for lumbar puncture
- Insert epidural needle through intervertebral spinous processes to the dural level (skin nick or pilot hole may be used to help with passage of the needle)
- Remove the needle stylet and observe for CSF drainage, advance slowly until CSF is returned
- A 5ml CSF sample to be taken from the needle
 - 3ml submitted for Cell counts with Differential and Chemistries
 - 2ml for biomarkers (cytokines) which must be stored in a -80° freezer until shipped to the core lab
- An additional level or re-positioned attempt can be made if no CSF is returned
- Do not perform excessive attempts to avoid potential complications such as CSF leakage, spinal headache or nerve root damage
- Insert guidewire and advance to low-mid thoracic spine, tracking dorsally

- Remove epidural needle and leave guidewire in place
- Using an OTW technique, advance catheter over the guidewire (with tension on the end of the guidewire to prevent further advancement)
- Upon reaching the guidewire tip, advance both the wire and catheter together until the catheter proximal inlet holes rest within the lumbar cistern (approximately L2-L3)
- When the catheter is in position remove the guidewire

If there is significant difficulty in gaining access, placing or positioning the catheter, abort the procedure and dress the wound per SOC. Those Subjects who have the procedure aborted due to an inability to gain access or obtain an acceptable position are classified as an “Attempt to Treat” subject and are followed according to the protocol through 2 day follow-up to assess the wound and potential adverse events related to the attempted access or catheter insertion. Subjects in the Attempt category are exited from the study after the protocol required 2 day follow-up visit.

It is highly recommended to have the Neurapheresis System assembled and prepped either prior to or while the catheter is being placed to minimize IR/OR time for the subject. However, if the system is not prepped completely by the time of catheter securement is complete, Investigators or center staff should carefully join the male and female ends of the catheter together to form a sterile loop to avoid CSF leakage while waiting to connect the catheter to the system. Do not overtighten the catheter hubs. The figure below demonstrates how to properly connect the catheter to maintain sterility of the catheter hubs.

[figure not shown]

Figure 7: Temporary Connection of the Catheter Male and Female Ends

Upon connection of the catheter to the system a flow test is required to ensure the connections are secure, the system has been appropriately set up and a flow loop has been established (refer to the IFU for proper system assembly and details on the required flow test). Following completion of a successful flow test, the catheter can be externally secured to the subject.

7.4.2 Guidance-Securing the Catheter/Dressing the Wound

Investigators are required to use a fixation device to secure the catheter to the subject to eliminate catheter movement and pullout. Commercially available devices (StayFix by Merit Medical) will be provided by the Sponsor to ensure availability. The fixation device contains a dressing but the choice of a topical antibiotic ointment is discretionary per the Investigator. Center personnel may also shave any excess hair from around the insertion site to assist with skin preparation for the application of the fixation device. Other institutional SOC surgical tape may be placed over the StayFix if preferred, however not underneath the StayFix.

The catheter is designed with extra length such that the pressure points can be avoided and that access to the system ports can easily be facilitated. Avoid positioning the extra catheter length over a bony prominence by taping the catheter to the Subject's abdomen or torso for easy access.

An ongoing dialogue with the MNeuro CFS will assure that the exteriorized catheter is properly positioned to optimize system functionality, however, guidance is provided below.

- Use the protocol required Stay-Fix device to dress the puncture wound site. Ensure that the orientation of the catheter and application of the dressing afford the least amount of bend/stress on the catheter (see Figure 8). The catheter should be positioned snugly over the blue support pad before securement.

[figure not shown]

Figure 8: Catheter Positioning within StayFix

- On smaller patients, a single coil with the catheter is to be created and may be secured with surgical tape.
 - While not required, previous Investigators preferred to cover the StayFix and single catheter coil with Tegaderm™ or OpSite™.
- For proper oversight of system functionality, it is imperative that the bifurcation (Y joint) and catheter luer hubs are visible at all times.
 - As such, they should not be hidden under the bed sheets or taped to bed rails
- It is necessary and appropriate to have a lengthy “tail” on the catheter.
 - When positioning the tail, it is recommended to tape the catheter to the torso, with a loop of coiled tubing to act as strain relief (see Figure 9).
 - Ensure placement of the catheter does not create a pressure point if the subject should roll over or move. Chux or gauze may be placed beneath the catheter hubs to further protect the connections.
- A second StayFix device may be used to further secure the coiled tubing to the patient's abdomen (Figure 9).

[figure not shown]

Figure 9: Catheter Fixation Device and Protective Dressing

7.4.3 OTB System Disposables Replacement

It is possible that a change of the OTB system disposables i.e., Filter and Flow Assemblies, Luer fill set and the waste bag, may be required during the Neurapheresis procedure. Change-out of the OTB system disposables can be driven by physical causes e.g., accidental cutting/crush of tubing or, driven by system data e.g., suspicious component behavior etc.

The Sponsor will track change outs of the disposables and the rationale for each action. Change-outs dictated by a component behavior may require return of the affected component to the Sponsor for analysis for product development purposes.

Change out of the OTB system disposables may be facilitated at the bedside; it is not necessary to return to the IR/OR, subject transfer is left to the discretion of the Investigator.

When changing the system disposables, Investigator will disconnect the catheter from the system and join the two ends (male→female) forming a sterile loop that maintains the sterility of the catheter ends (Figure 7). A sterile field should be established to connect the filter and flow assemblies and to facilitate priming of the system. The MNeuro CFS will guide center personnel in the catheter disconnection, component assembly, handing, and reconnection as needed based on the components being replaced. The IFU should also be referenced during this time for detailed instructions on disposable component replacement.

7.5 Neurapheresis Therapy

As this is an investigational system, Investigators and study staff expected to place, use or monitor the system will be trained in the applicable information, techniques and troubleshooting. Despite training, Investigators and applicable site staff should refrain from making medical decisions based on any data point or trend displayed on the Neurapheresis system interface and instead continue to rely on SOC devices or data.

The study catheter may remain in-dwelling for up to 72 hours (± 4 hr) in treated subjects during which study therapy can be completed. Neurapheresis therapy will be incrementally extended during the study such that, the first five (n=5) treated subjects enrolled under this protocol will have a maximum of 36 hours (± 4 hr) of Neurapheresis therapy (pump time) allowed during the 72 hours (± 4 hr) of catheter in-dwelling.

Following positive DSMB review of the data from the first five subjects, the remaining up to n=9 treated subjects (for a study total of N=30 Treated Subjects) will have no limit on maximum therapy time and instead be limited only by the maximum catheter in-dwelling time of 72 hours (\pm 4hr).

If the DSMB does not agree that it is safe to remove the Neurapheresis therapy limit after review of data from the first five subjects enrolled under this protocol, the maximum of 36 hours (\pm 4hr) of Neurapheresis therapy (pump time) will remain in place for the remaining subjects. s.

The sponsor will notify FDA, the IRB and clinical sites of the results from the DSMB review.

The start of catheter indwelling time is the time of catheter securement completion. The end of catheter indwelling time is marked by catheter removal and is not to exceed a total of 72-hours (\pm 4hrs). Center personnel must document required catheter times in the case report forms and medical record source as applicable.

Neurapheresis therapy start time is documented when study therapy is initiated. Therapy end is captured as the time the pump is stopped to allow for catheter removal. Study therapy will not be continuous for the 72-hours of catheter in-dwelling. Pausing of therapy may be required for SOC activities and potential fluctuations in the clinical status of the subject. The protocol also requires pausing of study therapy at the study required neuro checks and for study required CTs.

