Catheter Placement	
During catheter placement, an MNeuro clinical field specialist will be available to support the accurate assembly, placement, priming and testing of the system prior to beginning study therapy.
 
Fluoroscopy is required for catheter placement and as such it is expected to be performed in an IR/OR with preservative free saline available from the site to adequately prime the system.
 
Consent may be obtained prior to aneurysm securement to allow for catheter placement immediately following clipping or coiling in the same IR/OR session. Alternatively, consent may be obtained following aneurysm securement to ensure the patient continues to meet I/E criteria prior to enrollment or if applicable due to LAR availability. In this scenario, the subject must be brought back to the IR/OR in a separate session. The catheter must be placed ≤ 48 hours from ictus.

Neurapheresis Therapy	
The study catheter can remain in-dwelling for up to 72 hours ($\pm 4\text{hr}$) in treated subjects during which study therapy can be completed. Neurapheresis therapy

	
will be incrementally extended during the study such that, the first five (n=5) treated subjects enrolled under this protocol, will have a maximum of 36 hours ($\pm 4\text{hr}$) of Neurapheresis therapy (pump time) allowed during the 72 hours ($\pm 4\text{hr}$) of catheter in-dwelling.
 
Following positive DSMB review of the safety data from the first five subjects, the remaining up to n=9 treated subjects (for a study total of N=30 Treated Subjects) will have no limit on maximum therapy time and instead be limited only by the maximum catheter in-dwelling time of 72 hours ($\pm 4\text{hr}$).
 
If the DSMB does not agree that it is safe to remove the Neurapheresis therapy limit after review of data from the first ten subjects, the maximum of 36 hours ($\pm 4\text{hr}$) of Neurapheresis therapy (pump time) will remain in place for the remaining subjects.

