The PILLAR study protocol, under which subjects were enrolled, limited catheter in-dwelling time to 36 hours and total pump time (therapy time) to 24 hours. As can be seen in the table above, the average pump time was shorter than anticipated with only one subject receiving the complete 24 hour allotted time for study therapy. Despite this, clearance of red blood cells (RBCs) from the lumbar cistern was seen as noted in the table below. Longer pump times will be necessary for more complete blood clearance. Pre and Post-Neurapheresis total protein measures were also taken to account for removal of by-products from lysed blood.

PILLAR Post-Neurapheresis Outcomes

Outcome Measured N=13	Pre-Neurapheresis mean \pm STD	Post-Neurapheresis mean \pm STD	Percent Decrease of Means
Concentration of Total Protein	537.36 \pm 500.70 mg/dL	144.09 \pm 188.44 mg/dL	73.2%
Concentration of CSF Red Blood Cells (RBCs)	2.78e5 \pm 2.43e5 cells/ μ L	1.17e5 \pm 1.30e5 cells/ μ L	57.9%

Subjects were followed at 2-weeks and 30-days post-Neurapheresis. Other notable outcomes include; a mean of 12 days to discharge from the Neuro ICU with a range of [6 – 18 days]. By the 2-week visit, 38.5% (5/13) were discharged home which increased to 69.2% (9/13) by 30 days.

PILLAR Follow-up Outcomes

Follow-up Status N=13	Two Week Median [range]	30 Day Median [range]
GCS	15 [11-15]	NR*
WFNS	1 [1-5]	NR*
mRS	2 [1-5]	1 [0-4]
GOS	NR*	5 [3-5]
Barthel	NR*	100 [20-100]

*These neuro assessments were not required per protocol

Finally, the primary safety endpoint for the study was the assessment of adverse events associated with the placement of the catheter and operation of the system. As there were no (0) adverse events associated with the placement of the catheter and minimal, expected, non-serious adverse

events (as seen below) during Neurapheresis, the end points of this study were considered to have been met.

The adverse events (AEs) reported below is site reported and was also reviewed by the independent DSMB. While the AEs were reported as potentially related to Neurapheresis therapy, they are also known AEs for subarachnoid hemorrhage patients.

PILLAR Device or Procedure Related Adverse Events During Neurapheresis

Event	Timeframe	Serious Adverse Event (SAE)	Related to System	Related to Neurapheresis	n/N (%)
Headache with Vomiting	Neurapheresis	No	No	Yes	1/13 (7.7%)
Vomiting	Neurapheresis	No	No	Yes	1/13 (7.7%)

PILLAR Device or Procedure Related Adverse Events After Neurapheresis

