5.7.1 Subject Enrollment Classifications

All patients who provide written consent to participate in the study will be considered enrolled study subjects, however not all subjects will contribute to the enrollment cap of N=30 Treated Subjects. Only treated subjects, as defined below, will contribute to the enrollment cap. As such, it is expected that up to 40 subjects may be enrolled to meet the enrollment cap. FDA, IRBs and Investigational sites will be notified when enrollment is complete.

Intent to Treat Subjects:

- Subjects who provide written informed consent but do not have placement of the study catheter attempted. This would include placement tools such as the epidural needle and guidewire. Intent to Treat subjects will be exited immediately. They will not count towards the enrollment cap of N=30 treated subjects. Only enrollment and study exit data will be collected in the study database.

Attempt to Treat Subjects:

- Subjects who provide written informed consent and have any portion of the catheter placement procedure attempted (including the epidural needle and guidewire) but placement was unsuccessful. Attempt to Treat subjects will be followed through 2 days post-attempt for safety then will be exited. They will not count towards the enrollment cap of N=30 treated subjects. They will be included in the analysis of safety endpoints but will not be included in the analysis of efficacy endpoints. Enrollment, catheter placement attempt, 2 day follow-up and study exit data will be collected along with any adverse events or protocol deviations if applicable.

Treated Subjects:

Subjects who provide written informed consent, have successful placement of the study catheter and had Neurapheresis initiated. These subjects will be followed out to 30 days according to the study protocol then exited. They will count towards the enrollment cap of

N=30 treated subjects and used in all analyses. All study data through the 30 day follow-up will be collected.

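### The DSMB review that can remove the 36 h pump-time limit counts five subjects in whom therapy was started, and requires none of them to have been observed near 36 h

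*Combined protocol and SAP*

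**What the plan says.** Section 7.5 describes therapy as being extended in steps. In the first step, "the first five (n=5) treated subjects enrolled under this protocol will have a maximum of 36 hours" (±4 h) of pump time. The trigger for the next step is "Following positive DSMB review of the data from the first five subjects", after which the remaining subjects "will have no limit on maximum therapy time and instead be limited only by the maximum catheter in-dwelling time of 72 hours" (±4 h). If the DSMB does not agree, the 36 h limit stays for all remaining subjects. No second review is described.

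The synopsis has the same trigger: "Following positive DSMB review of the safety data from the first five subjects, the remaining up to n=9 treated subjects". However, its sentence on what happens if the DSMB does not agree refers to the first ten subjects, where Section 7.5 says five.

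Under Section 5.7.1, Treated Subjects are those who consent, "have successful placement of the study catheter and had Neurapheresis initiated". No minimum hours are given. Section 13.3 gives event-based enrollment holds and refers to a charter; it sets no exposure condition for this review. The only minimum exposure in the plan is in Section 10.2, where enrollment stops once 30 subjects have had at least 16 h of therapy.

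Section 2.1 reports that the PILLAR protocol "limited catheter in-dwelling time to 36 hours and total pump time (therapy time) to 24 hours", with "only one subject receiving the complete 24 hour allotted time for study therapy". Section 2.2 says that 16 subjects have been treated under an earlier version of this protocol, and does not give their pump hours.

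**The concern.** A stepped extension is informative if the subjects at one step are observed at or near that step's limit before the next is opened. Here the rule counts subjects, not exposure. Five subjects who each stopped after a few hours would satisfy the wording, yet would tell the DSMB almost nothing about 36 h.

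Early stopping and long pauses are realistic. The protocol requires pauses for neurological checks, CTs, CSF sampling and adverse pressure gradients, and Section 7.5.2 lists nine conditions that end therapy. PILLAR shows how far received hours can fall below permitted hours.

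At stake is the basis for removing the limit in up to nine subjects. Because only one review is described, thin exposure leaves the DSMB two choices: extrapolate from shorter exposures, or leave the limit in place for everyone who follows. The plan already treats hours as important when it decides when to stop enrollment, but not in this safety step.

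**Working it through.** **The plan's own count.** 16 already treated (Section 2.2) + 5 under the limit + up to 9 afterwards (Section 7.5) = 30. This reproduces the stated N=30. It also confirms that the five are new subjects, separate from the 16.

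**Permitted and received hours in PILLAR (Section 2.1, N=13).**
- Mean pump time 15:07 = 15.12 h; limit 24 h; 15.12/24 = 0.63 of what was permitted. Range 5:32 to 24:00.
- Share reaching the limit: 1/13 = 7.7%, exact 95% confidence interval 0.2% to 36%.

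**Does that share carry over?** The targets differ.
- PILLAR: 24 h of pump time in 36 h of in-dwelling, 24/36 = 0.67.
- This study: 36 h in 72 h, 36/72 = 0.50.
- Mean in-dwelling in PILLAR was 30:23 = 30.38 h, so pump time was 15.12/30.38 = 0.498 of in-dwelling time.
- If that ratio held for a full 72 h: 0.498 × 72 = 35.8 h, about equal to the limit. With a roughly symmetric spread, about half of subjects might reach it.
- If subjects used only PILLAR's fraction of permitted in-dwelling time (30.38/36 = 0.84): 35.8 × 0.84 = 30.2 h, below the limit.

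The 36 h target is thus easier than PILLAR's, and 1/13 is probably too low a share for this study. The documents do not give the right value, so a range is needed.

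**Number of the five who reach the limit.** Let p be the share who do, with subjects independent. Then P(none) = (1−p)^5 and P(at most one) = (1−p)^5 + 5p(1−p)^4.

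| Assumed p | P(none of five) | P(at most one of five) |
|---|---|---|
| 1/13 | 67% | 95% |
| 20% | 33% | 74% |
| 40% | 8% | 34% |
| 50% | 3% | 19% |

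For example, at p = 0.5: 1/32 + 5/32 = 6/32 = 19%.

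The formula also applies if a looser threshold counts as near the limit (for instance 32 h, the lower edge of the ±4 h tolerance); p is then the share reaching that threshold.

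**The case against.** - **The PILLAR rate is not a forecast.** A reader might infer from 1 of 13 that the five will probably include nobody at 36 h (67%). The documents do not support that: the target here is a smaller fraction of in-dwelling time, and PILLAR's own pump-to-in-dwelling ratio is compatible with about half reaching it, which gives 3%. This objection stands, and it is why only a range is shown.
- **Sixteen subjects have already been treated in this study.** They are the closer and larger cohort, and some may have had long exposures. That is possible, but their hours are not in these documents, and Section 7.5 ties the decision to the first five under this version.
- **The DSMB is free to refuse.** It may decline to lift the limit if exposure is thin, and its charter, which is not among the documents, may contain an exposure condition. This lowers the risk. It does not repair a protocol rule that can be met without relevant data, or the absence of a second look.
- **No capped stage can show data beyond its cap.** A reader might fault the review for having none above 36 h (40 h with tolerance). That is true of any stepped design and is not the defect; the gap is at the limit itself.
- **Five subjects are few in any case.** With zero events in five, the one-sided 95% upper bound on risk is 1 − 0.05^(1/5) = 45% even with full exposure. That bound belongs to any five-subject review in a feasibility study without hypotheses, so it does not measure this problem.
- **Sections 7.5 and 5.7.1 do not conflict.** They use the Treated category consistently. The category simply does not suit this purpose.

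**Conclusion.** The point holds as a gap in the rule, and it should be corrected. As written, the limit can be removed after a review in which no subject came near 36 h, because Treated status requires only that therapy began and no exposure condition is stated anywhere in the protocol.

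How likely that is cannot be determined from the documents. The chance that at most one of five reaches the limit runs from 95% (share 1/13) to 19% (share 50%), assuming independent subjects and treating the share as unknown. Even at the favourable end, about one review in five would rest on one subject or none at the limit. The documents do not support the stronger inference that the review will probably be empty.

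Two things could change the conclusion: an exposure condition in the DSMB charter, in which case a cross-reference is enough, or long achieved hours among the 16 earlier subjects, if these are formally part of the review.

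**What to change.** 1. In Section 7.5 and the synopsis, base the DSMB review on subjects evaluable for exposure at the limit under review, rather than on any five subjects in whom therapy was started. The sponsor and DSMB should define evaluability, the number needed, and what follows if too few are evaluable, since only one look is now described. No therapy limit or clinical rule is proposed here.
2. Give the DSMB each subject's achieved pump and in-dwelling hours, including those of the 16 earlier subjects. The system already logs its run data, and catheter and therapy times are already documented.
3. Reconcile the synopsis (five subjects for lifting the limit, ten for not lifting it) with Section 7.5 (five in both places).
4. Reconcile the N=30 Treated count in Section 5.7.1, which has no minimum hours, with the 16 h condition for stopping enrollment in Section 10.2.

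The cost is wording in the protocol and charter, plus a listing for the DSMB. The downside is that the decision may come later, leaving fewer subjects to be treated after it.
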